This is a randomised, open-label, non-inferiority clinical trial comparing two parallel arms: a standard care arm using Amsler Grid home monitoring (PRN), and an intervention arm using the CRYSTALSIGHT gaze-tracking system (PRN+). A total of 220 (Singapore – 60, United Kingdom – 80, United States – 80) participants will be randomised in a 1:1 ratio. Participants in the intervention arm will self-administer biweekly CRYSTALSIGHT tests at home, while those in the control arm will use the Amsler Grid. Both arms will attend monthly clinic visits for standard evaluations, including VA, BCVA, and OCT. Alerts generated by the CRYSTALSIGHT system based on deviation thresholds will trigger early clinic recall for confirmatory imaging and potential re-treatment.

[figure not shown]

Figure 4 Details of the home-use clinical trial study design. The trial objective: show that PRN+ is non-inferior to standard of care PRN with better VA/VF outcomes

Development of CRYSTALSIGHT cutoff scores should have been conducted in the cohort-1 1 study [NCT: NCT06518512] (Analysis). This Phase 2 should be the application of validated cut-off scores. The second aim will be to compare the accuracy of CRYSTALSIGHT and Amsler, and sensitivity and specificity check.

In addition to identifying CRYSTALSIGHT visual risk prediction cut-off scores, detection yields, and diagnostic Performance indicators will also be evaluated. Progression to CNV was

OCCUTRACK

determined by the investigator, based on standardised OCT confirmation. At the clinical trial site, these events were confirmed by gradings conducted by masked, certified independent personnel who did not know the treatment assignment. Events from both arms are graded using a standardised protocol.

[figure not shown]

Figure 5 In Cohort 2, home-based score deviation detected, study coordinator will schedule hospital checkup immediately. If CRYSTALSIGHT correctly detects wet AMD recurrence confirmed by OCT, subject exits the study.

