The CRYSTALSIGHT eye tracking system is a medical monitoring system used to treat age-related macular degeneration (AMD). AMD is a disease that affects the macula, the part of the eye responsible for central vision. CRYSTALSIGHT helps people with AMD maintain their quality of life by improving their ability to perform everyday activities.

[figure not shown]

Figure 7 Cohort 1 results of a single test subject showing the correlation of OCT scores to CRYSTALSIGHT at two clinic visits.

[figure not shown]

Figure 8 Population of cohort-1 study, each box represents a tested eye (total 36 eyes in this plot), each dot represents a single clinic visit, green = CRYSTALSIGHT, blue = OCT.

OCCUTRACK

	Cohort 1	Cohort 2
Trial objectives	Verify OCT versus CRYSTALSIGHT correlation (threshold score)	wAMD/DME recurrence detection - (intervention alerts)
Device	CRYSTALSIGHT camera with Tobii ET5L	CRYSTALSIGHT camera only OR Digitized amsler Grid
Physician interaction	Four times: 1. Registration 2. First follow up 3. 2 nd follow up 4. Exit	PRN* regimen: 1. Registration 2. Monthly clinic visits 3. Intervention 4. Exit *(PRN scheduled clinic visits will proceed normally)
Size	100	220
Intended use	Clinic based	Home-based

In Cohort-1, the CRYSTALSIGHT system will be used in a clinical setting under the guidance of a trained healthcare professional to confirm the correlation between CRYSTALSIGHT and OCT in the same study participant longitudinally and establish a threshold for "deterioration."

Recruitment

- Eligibility Diagnosis:** The PI determine eligibility and will inform a potential participant (diagnosed with wAMD who is on a treatment regimen) to determine if CRYSTALSIGHT is an appropriate monitoring option.
- Enrolment:** If CRYSTALSIGHT is deemed appropriate for the patient, the PI or study coordinator will enroll the patient in the trial for the device and provide the patient with instructions for using the device.
- Training:** the study coordinator trains the participant on a CRYSTALSIGHT device to familiarise the patient with the device and ensures that the patient understands and follows the rules for home use.
- Initial monitoring:** The PI will start the participant on self-monitoring with CRYSTALSIGHT twice a week and monitor the participant's baseline gaze performance via the CRYSTALSIGHT electronic database.

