Follow Up Visit #7 Month 7 (+/- Four weeks)	Standard Routine Care 
 • Visual Acuity (VA) • BCVA (Optional) • Optical Coherence Tomography (OCT) • Colour Fundus Photography • Clinical Consultant Review • Intravitreal Injections (IVT) (Optional)
Follow Up Visit #8 Month 8 (+/- Four weeks)	Standard Routine Care 
 • Visual Acuity (VA) • BCVA (Optional) • Optical Coherence Tomography (OCT) • Colour Fundus Photography • Clinical Consultant Review • Intravitreal Injections (IVT) (Optional)
Follow Up Visit #9 Month 9 (+/- Four weeks)	Standard Routine Care 
 • Visual Acuity (VA) • BCVA (Optional) • Optical Coherence Tomography (OCT) • Colour Fundus Photography • Clinical Consultant Review • Intravitreal Injections (IVT) (Optional)
Follow Up Visit #10 Month 10 (+/- Four weeks)	Standard Routine Care 
 • Visual Acuity (VA) • BCVA (Optional) • Optical Coherence Tomography (OCT) • Colour Fundus Photography • Clinical Consultant Review

OCCUTRACK

Follow Up Visit #11 Month 11 (+/- Four weeks)	Standard Routine Care 
 • Visual Acuity (VA) • BCVA (Optional) • Optical Coherence Tomography (OCT) • Colour Fundus Photography • Clinical Consultant Review
Study Exit Visit #12 Month 12 (+/- Four weeks)	Standard Routine Care 
 • Visual Acuity (VA) • BCVA (Optional) • Optical Coherence Tomography (OCT) • Colour Fundus Photography • Clinical Consultant Review • Intravitreal Injections (IVT) (Optional)

Locations

Three study sites are proposed:

1. [name], PLLC, New London, United States
2. The Princess Alexandra Eye Pavilion in Edinburgh, Scotland, United Kingdom
3. Tan Tock Seng Hospital, Singapore

Timeframe

Estimated Start Date: June, 2025

Estimated Completion Date: August, 2026

Eligibility

Inclusion / exclusion criteria of this study are as follows.

Participation Requirements:

Genders: Both

Minimum Age: 55

Healthy Volunteers: No

Inclusion criteria

1. Subjects in the age group ≥ 55 to 99 years old.
2. Both genders
3. Able to understand verbal spoken instructions in British/American English, Chinese or Bahasa Melayu and demonstrate device functionality and implementation.
4. Able to turn on and connect the CRYSTALSIGHT device to a computer independently or with the help of family.

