4. Follow best practices: The participant should follow best practices when using the device, including placement, head position, and attention to stimulation targets on the screen.

By following these steps, a new user can master the CRYSTALSIGHT health monitoring device and effectively manage their AMD condition.

How are they going to get the device

One CRYSTALSIGHT boxed unit will be signed over to the study participant to bring home after the recruitment administration is done during the regular clinic check-up and when the participant has agreed and signed the Informed Consent Form (ICF) to be included in the study.

System reminders

A study coordinator will monitor the electronic records system and will call the participant to conduct a self-test at home if they miss the test by 1 day. A system

OCCUTRACK

reminder will automatically send a message and email to remind the user to take the test if a scheduled self-test is missed by a day.

Results and reporting: The results of the tests will be transmitted to a secure server where they will be analyzed by the principal investigator and study coordinator. If any changes in vision are detected, the subject will be contacted by the study coordinator and a follow-up appointment will be scheduled.

Sample size calculation:

According to the workflow, all participants will have routine visits to clinic with OCT scans performed once every 4 weeks. Participants randomised into the CRYSTALSIGHT group will have measurements taken twice a week if the testing results are all negative. In case of a positive result with CRYSTALSIGHT, another test will be done on the next day. Participants will be recalled for review after two consecutive positive results are presented. Depending on the pathology presented on the OCT scan, IVT may be given for disease management. On the other hand, participants randomised into the Amsler Grid group will be evaluated by Amsler Grid and by OCT.

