For participants in the CRYSTALSIGHT group, each participant will have a testing result by CRYSTALSIGHT and by OCT every 4 weeks or less if the positive result triggers a clinical visit. The result is considered correct if it is consistent with the findings of the OCT scan. During the one-year study period, the total number of correct results generated by CRYSTALSIGHT will be counted and the accuracy for these participants will be calculated as number of correct results divided by the total number of clinical visit. For participants in the Amsler Grid group, the accuracy for each participant will also be calculated.

According to literature, the accuracy of Amsler Grid in detecting disease activity was about 80%, we will assume that CRYSTALSIGHT has the same accuracy. For the Singapore population, we will also assume that standard deviation of the accuracy to be 0.12 and setting the maximum allowable difference in accuracy (non-inferiority margin) between the two groups to be 0.09, with one-sided type 1 error of 0.025 and a power of 0.8, a total of 52 participants will be required (26 per group). Considering of 15% attrition rate, a total of 60 participants will be required.

For global study, we assume a higher standard deviation of the accuracy to be 0.21 and a dropout rate of 21%, a total of 220 participants will be required (110 per group).

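### The Figure 5 exit on a correct CRYSTALSIGHT detection is not reconciled with the Month 12 schedule or the one-year accuracy count, and can bias the accuracy ratio

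*Protocol*

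**What the plan says.** In Study Design, the Figure 5 caption reads: "If CRYSTALSIGHT correctly detects wet AMD recurrence confirmed by OCT, subject exits the study". Only the device is named.

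The Study Schedule Table lists monthly visits and a single exit, "Study Exit Visit #12 Month 12 (+/- Four weeks", with no earlier exit branch.

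The Sample size calculation section defines the quantity on which the trial is sized. "During the one-year study period, the total number of correct results generated by CRYSTALSIGHT will be counted", and each participant's accuracy is "calculated as number of correct results divided by the total number of clinical visit". The Amsler arm's accuracy is to be calculated per participant too. The same section has results arising "every 4 weeks or less if the positive result triggers a clinical visit".

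Two places lean towards an event-driven end. The description of study phases has home testing run until the device registers a deterioration, followed by a follow-up phase. The Cohort 1 / Cohort 2 table lists, for Cohort 2, "3. Intervention 4. Exit *(PRN scheduled clinic visits will proceed normally", in a column whose device entry is "CRYSTALSIGHT camera only OR Digitized amsler Grid".

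**The concern.** The exit is triggered only by a correct result. Under it, the last scored visit of every participant who leaves early is a correct one, while a participant whose recurrence the device misses stays in and goes on being scored. The endpoint is the mean of per-participant ratios, so a ratio over few visits counts as much as one over twelve. Such a stopping rule can move the mean even when the device's performance at a visit is unchanged.

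If the rule applied to the device arm alone, the shift would pass straight into the between-arm difference and be set against the 0.09 margin. An analysis plan could not repair this afterwards, because the visits of participants who have left do not exist. The protocol text does not settle whether the exit applies, or to whom.

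**Working it through.** **The plan's own figure.** Inputs from the Sample size calculation section: accuracy 0.80 in both arms, margin 0.09, SD 0.21, one-sided 0.025, power 0.80, dropout 21%. Per arm: 2 × ((1.96 + 0.8416) × 0.21 / 0.09)² = 85.5, so 86. Total 172 / 0.79 = 218, against 220 stated. The figure reproduces.

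**Assumptions, not in the protocol.** Sensitivity = specificity = a (0.80, or 0.71 for a device worse by exactly the margin). Twelve scored visits, independent. Visit 1 is scored but recurrence-free, because inclusion criterion 5 asks for no signs of recurrence at entry and recurrence is defined as a change. At each of the 11 later visits recurrence has probability h = 3, 5, 10 or 20%; then 1 − (1 − h)^11 = 28, 43, 69 or 91% of participants have at least one in the year.

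**Mean ratio with exit at the first true detection.** Let q = h·a and c = (1 − h)·a / (1 − q). Then

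mean = Σ over k = 2..12 of (1 − q)^(k−2) · q · (a + (k − 2)c + 1)/k, plus (1 − q)^11 · (a + 11c)/12.

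Without the exit the mean is a.

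**Error at the margin.** SE = 0.21 × √(2/86) = 0.0320. False-claim rate = 1 − Φ(1.96 − (difference + 0.09)/SE). For h = 10%, device arm only: q = 0.071, mean 0.7290, difference 0.7290 − 0.80 = −0.0710, and (−0.0710 + 0.09)/0.0320 = 0.59, giving 8.6%.

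| h per visit | Mean at a = 0.80 | Rise | Mean at a = 0.71 | Error, device arm only exits | Error, both arms exit |
|---|---|---|---|---|---|
| 3% | 0.8052 | 0.005 | 0.7168 | 4.0% | 2.8% |
| 5% | 0.8082 | 0.008 | 0.7207 | 5.2% | 3.0% |
| 10% | 0.8143 | 0.014 | 0.7290 | 8.6% | 3.5% |
| 20% | 0.8221 | 0.022 | 0.7401 | 15.4% | 4.3% |

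**A more coherent model.** The formula takes its shift from identical participants but divides by an SD of 0.21, which implies that participants differ. Letting participant accuracy follow a beta distribution (concentration 3.77, which gives SD 0.21 in the control arm), with 86 per arm and 20,000 simulated trials per run, the device-arm-only error is 3.5–3.6, 4.1–4.8, 6.1–6.7 and 10.5–10.8% over repeat runs. With both arms exiting it is about 3–4%.

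**If recurrence can occur at every scored visit, Visit 1 included.** The rise at a = 0.80 is 0.009, 0.015, 0.026 and 0.043, and the device-arm-only error is about 5, 6, 13 and 26% in the SD-matched model.

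**Direction.** With sensitivity 0.90, specificity 0.75, h = 10% and active disease persisting with probability 90% per visit, full follow-up gives a mean of 0.796 and the exit lowers it to 0.779. With 0.50 and 0.85 and the same persistence, the exit raises it by 0.055.

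**The case against.** Figure 5 itself is not shown, and a caption about the device naturally names only the device. The Cohort 2 column puts Exit after Intervention and covers both devices, and the phase description supports testing that ends at a detection. So an exit in both arms may be what was meant, with Month 12 and the one-year period as maxima. The ratio's denominator is that participant's own visits, so it can be computed over shorter follow-up. This stands in part: under a two-arm exit most of the bias cancels. But the protocol states neither the maximum nor the matching exit.

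A reader might infer a wider contradiction, taking in the table's note that scheduled visits go on normally and the statement that "all participants will have routine visits to clinic with OCT scans performed once every 4 weeks". Both are weak evidence. The note can mean routine care continues after study exit, and the sample size text merely does not mention an exit.

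A reader might also infer that the exit must favour the device, or that the error reaches tens of percent. The documents support neither. The sign depends on sensitivity, specificity and how long disease stays active, none of which is given. The largest figures need recurrence possible at the baseline visit, an exit in one arm only, and a recurrence rate for which the protocol offers no basis. Finally, the effect belongs to the mean of per-participant ratios: with independent visits and equal participants, a pooled ratio stays at 0.800.

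**Conclusion.** The point holds as an unreconciled rule with a possible bias. The caption's exit, the Month 12 schedule and the one-year count are not brought together anywhere, and the exit, if followed, ties the length of scoring to a correct device result.

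Where recurrence cannot occur at Visit 1, the device-arm mean shifts by about 0.005 to 0.022, or 6 to 24% of the 0.09 margin (0.005/0.09 and 0.022/0.09). The error at the margin goes from 2.5% to about 3.5–11% in the SD-matched model if only the device arm exits (4.0–15.4% by formula), and to about 3–4% if each arm exits on its own true detection. These figures rest on assumed sensitivity and specificity of 0.80, independent visits and an assumed 3–20% recurrence per visit. They are larger if recurrence can occur at every scored visit, and the sign can reverse. Confidence is medium: the gap in the text is plain, the size is not.

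**What to change.** Reconcile the Figure 5 caption with the Study Schedule Table and with the one-year count in the Sample size calculation section. State that accuracy is scored in both arms over the same window, the already scheduled monthly visits to Month 12, whatever the home test shows and even if study use of the device ends earlier. In that last case, also say how a visit without a home result is scored, identically in both arms.

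Scoring past a first recurrence needs one further definition: the reference value against which a later change in retinal thickness or acuity is judged. The protocol does not give one.

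The cost is protocol wording, that reference definition, and continued data from visits already scheduled for participants who would otherwise have left. No extra patients are needed: 172 / 0.79 = 218, so 220 stands. Which exit or treatment rule applies clinically is for the sponsor to reconcile.

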This study will use the CRYSTALSIGHT system in an unsupervised home setting. Participants will perform biweekly self-monitoring with the CRYSTALSIGHT device. The threshold algorithm will be implemented and validated with subjects. Threshold information from Cohort 1 will thus be incorporated into the Cohort 2 intervention measures. Figure 5 illustrates the function of the CRYSTALSIGHT score as the basis for an intervention measure: an earlier-than-expected clinic visit should be scheduled immediately for clinic vision testing and urgent anti-VEGF administration.

Pro Re Nata (PRN): Standard treatment (control arm)

Participants randomized to the standard treatment arm received specific instructions from investigators for self-monitoring of vision at home to detect progression of AMD. Aids such as the Amsler grid. This group is referred to below as the standard treatment group. If participants experienced symptoms, they were instructed to call their clinical centre immediately and schedule an appointment within 72 hours.

PRN+: Home monitoring device (device arm)

In addition to the same standard of care instructions, participants will receive a CRYSTALSIGHT home monitoring device with instructions for installation and use. This arm is referred to below as the device arm. In cases where baseline measurements could not be obtained due to a pre-existing visual field defect in at least one study eye, participants returned the device and continued monitoring with standard treatment only but were still included in the final analyzes in the intent-to-treat (ITT) cohort as part of the device arm.

Participants were encouraged to use the device twice a week, and results were automatically transmitted via internet cloud to a Occutrack's data monitoring center. If testing of the device indicated a change from baseline measurements, an alert was sent from the monitoring center to the participant's clinical center, prompting staff to schedule an appointment with the study ophthalmologist within 72 hours.

This study is an open-label, randomized study designed to evaluate the safety and efficacy of the CRYSTALSIGHT device when used by patients in their own homes. The study will

OCCUTRACK

recruit a group of patients who meet certain eligibility criteria and provide them with the CRYSTALSIGHT device for use at home.

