The Cohort 2 study typically several phases, including a screening phase to identify eligible patients who could be recruited patients exiting the anti-VEGF injection clinic. The phases are:

- **Training:** a training phase for the device to ensure that patients know how to use the device properly, a testing phase in which patients use the device to monitor their vision condition using the CRYSTALSIGHT device over a period of time until the device detects deterioration in vision and meets the criteria for deterioration established by the Cohort 1 results, and a follow-up phase to assess results and obtain feedback from patients.
- **Monitoring:** During the study, patients will be asked to follow the specific protocols and guidelines for use of the CRYSTALSIGHT device, such as completing the bi-weekly regular testing. Patients will also be asked to report or provide feedback on any adverse events or problems encountered while using the device.
- **Intervention:** Should the CRYSTALSIGHT device determine that a threshold for vision deterioration has been reached (delta deviation of 10 points from the nominal baseline), the patient/participant will receive a notification from the prescribing physician and the electronic alert system via email to the subject's personal mobile device instructing them to schedule an appointment for confirmation OCT -A that the subject's wet AMD has recurred, see Figure 6 below.

[figure not shown]

Figure 6 True-False confusion matrix of cohort-2 will require OCT confirmation of wet AMD disease recurrence that was detected by CRYSTALSIGHT.

This cohort 2 intervention study is designed to collect data on the safety and efficacy of the device, including information on the accuracy, reliability, and ease of use of the device. The study may also examine the impact of the device on patient outcomes, such as changes in visual status or quality of life.

Once the study is complete, the data will be analyzed to determine if the device is safe and effective for home use. If the results are positive, the device can be submitted to the FDA for approval and made available to patients who need it.

OCCUTRACK

Cohort-2 study relationship to the cohort-1

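### The only adverse-event request reads as addressed to CRYSTALSIGHT users during use, so the safety conclusion has no control-arm background rate for solicited events

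*Protocol*

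**What the plan says.** Only the protocol is at hand. Under the PRN+ device-arm heading it describes an open-label randomised study "designed to evaluate the safety and efficacy of the CRYSTALSIGHT device when used by patients in their own homes". After Figure 6 it adds that, once the study is complete, "the data will be analyzed to determine if the device is safe and effective for home use".

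The one request for adverse events is in the Monitoring bullet of the study phases: "Patients will also be asked to report or provide feedback on any adverse events or problems encountered while using the device". The sentence just before it concerns following the guidelines for CRYSTALSIGHT and completing its regular tests. The only other use of the word adverse, under Eligibility, labels wet AMD recurrence as the outcome.

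The Study Schedule Table lists visual acuity (VA), optional BCVA, OCT, fundus photography, consultant review and, at most visits, injections. It has no adverse-event item. Controls are told to call their centre if they have symptoms, and the device arm gets that instruction too: "In addition to the same standard of care instructions, participants will receive a CRYSTALSIGHT home monitoring device".

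A device alert can lead to treatment. The Study Design text says that "an earlier-than-expected clinic visit should be scheduled immediately for clinic vision testing and urgent anti-VEGF administration", and the sample size section says: "Depending on the pathology presented on the OCT scan, IVT may be given for disease management". The Figure 5 caption then states: "If CRYSTALSIGHT correctly detects wet AMD recurrence confirmed by OCT, subject exits the study".

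**The concern.** A count of adverse events among device users is hard to interpret without knowing how many such events similar patients report without the device. This trial has a randomised control arm that attends monthly and could supply that background rate. As written, the protocol asks one group for adverse events and, on the natural reading, does not ask the other.

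Two things are at stake. The statement on safety for home use would rest on device-arm reports alone. If someone later compared reports between arms, part of any difference would come from unequal asking. How events are elicited is fixed by the protocol, and a statistical analysis plan cannot recover reports that were never requested.

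**Working it through.** **1. The plan's own sample size, used below.** Inputs from the sample size section: SD 0.21, margin 0.09, one-sided type 1 error 0.025, power 0.80, dropout 21%. Per group, n = 2 × SD² × (z₀.₉₇₅ + z₀.₈₀)² / margin² = 2 × 0.21² × (1.960 + 0.842)² / 0.09² = 85.5, rounded up to 86. The total is 172, and 172 / 0.79 = 218. The t-based version gives 87 per group, and 174 / 0.79 = 220. The stated 220 (110 per group) reproduces. After dropout, 110 × 0.79 = 87 per arm.

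**2. What each arm is asked or examined for.**

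| Channel | Control arm | Device arm |
|---|---|---|
| Adverse-event request (Monitoring bullet) | not on the natural reading | yes, during use |
| Adverse-event item in the visit schedule | 0 of 12 | 0 of 12 |
| Instruction to call with symptoms | yes | yes |
| VA, OCT, fundus photography, consultant review | 12 of 12 | 12 of 12 |

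Only the first row differs. The lower two rows give both arms the same route to detecting vision loss and recurrence.

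**3. Direction of any distortion.** Suppose the true event share r is the same in both arms, and shares d (device) and c (control) of events are captured. The reported difference is r × (d − c). The shared channels contribute to both d and c, and the extra request can add only to d. So d is plausibly at least as large as c, and the reported difference leans towards more events in the device arm. The protocol gives neither d nor c, so no size follows.

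**4. What equal asking would deliver.** The 95% CI half-width for the difference is 1.96 × √(2r(1 − r)/n). The event shares are assumptions, since the protocol gives none.

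| Assumed event share | n = 110 per arm | n = 87 per arm |
|---|---|---|
| 5% | ±5.8 points | ±6.5 points |
| 10% | ±7.9 | ±8.9 |
| 20% | ±10.6 | ±11.9 |
| 30% | ±12.1 | ±13.6 |

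For example, at 20% and n = 110: 1.96 × √(0.32/110) = 0.106.

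**5. Why follow-up time is needed.** The Figure 5 caption states exit after a confirmed CRYSTALSIGHT detection. If a share e of the device arm exits, on average halfway through, that arm's follow-up is shorter by e/2. Assumed values of e of 10%, 30% and 50% give 5%, 15% and 25%. Raw counts would not be on an equal footing.

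**The case against.** **No comparison is promised.** The protocol does not call the safety conclusion comparative, and safety is not among the primary or secondary objectives. Problems of handling a camera and screen have no counterpart in controls, so asking users about them is right. This stands, and a reader who infers that a promised between-arm safety analysis is invalid goes further than the text allows. What remains is that safety is an aim of a randomised study and the available background rate is not collected.

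**The wording is not expressly restricted.** The sentence says patients without naming an arm, the closing phrase could attach to problems alone, and the Cohort 2 device row also lists a digitised Amsler grid. This stands in part, so the restriction is a reading. It is the most natural one, because the preceding sentence and the rest of that section use the word device for CRYSTALSIGHT.

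**Other channels exist.** Symptom calls and monthly consultant review reach both arms, and the Training bullet mentions a follow-up phase for patient feedback. A reader might infer that harm in controls would go unseen; the documents do not support that for vision loss or recurrence. But none of these channels is stated to include an adverse-event question, and the feedback phase is described within device use. Consent pages were not available, so any reporting instruction there could not be checked.

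**Returned devices.** Where no baseline could be obtained, "participants returned the device and continued monitoring with standard treatment only but were still included in the final analyzes". It is tempting to count these participants as a second gap. Their home exposure is likely to be minimal, so they add little to a device-safety question.

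**Conclusion.** The point holds as a minor data-collection issue. Followed as written, the protocol yields no control-arm background rate for solicited adverse events against which to read the safety conclusion. This rests on the natural reading of the Monitoring sentence and on the absence of an adverse-event item at all 12 visits. The primary accuracy analysis is unaffected.

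A reader might infer that the bias could equally favour either arm, or be of a particular size. The documents give no capture rates, so no size can be stated. Since the extra request is the only channel that differs, higher device-arm reporting is the more plausible direction, which would work against the device.

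A reader might also infer that equal asking would capture harm from alert-triggered injections. It largely would not: a confirmed alert means exit, so the consequences of an injection given at that visit fall outside follow-up.

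**What to change.** Replace the Monitoring sentence with:

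> *Adverse events are asked about in the same way at every monthly visit, and at any recall visit, in both arms; problems of using the device are recorded separately.*

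Report adverse events by assigned arm, with participant-months of follow-up beside the counts. Recall visits may be more frequent in the device arm, so note the type of visit at which each event was reported; the answers from monthly visits can then be read on their own.

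The cost is one protocol sentence, one extra question per visit and one table. Sample size, visits, treatment and exit rules do not change. The comparison stays imprecise, as step 4 of the working shows. Events after an injection at the exit visit remain uncaptured, and the change should not be presented as closing that gap.
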